8.5.7 RANDOMIZATION

Only subjects who have undergone standard chest CT-scan to determine if the aortic stenosis can be replaced with an available Perceval valve (size), and is potentially suitable for mini-sternotomy, may be randomized. For each subject the randomization will be performed based on the randomization list after enrollment and before valve operation, specifically after CT scan and surgical approach ("full sternotomy" or "mini-sternotomy") has been determined, to minimize bias.

Subjects will be randomly assigned in equal numbers (1:1) to one of two treatment arms. The blocked randomization list will be performed before the study start. The randomization will be stratified with 2 stratification factors, by country and by surgical approach (full sternotomy” or “mini-sternotomy”).

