8.7 PROCEDURES

8.7.1 CLINICAL TRIAL RELATED PROCEDURES

All qualified personnel performing selection, implantation and/or follow-up procedures must be trained on the trial protocol. The trial devices should be used in accordance with the corresponding instructions for use.

Detailed instructions on the type and process of data to be collected for the study and how to fill in the eCRFs will be provided to the Investigators during dedicated meetings.

Screening & enrolment

Subjects must be informed about the study including the potential risks and benefits prior to enrollment. Only those subjects who voluntarily provided written informed consent to participate, in a timely manner will be eligible for enrollment.

The following procedures must be conducted BEFORE inclusion:

- Determination of patient eligibility for biological standard surgical aortic valve replacement.
- Echo examination to assess severity of aortic stenosis (e.g. blood flow velocity, EOA)
- CT-scan
- Evaluate subject eligibility based on the inclusion and exclusion criteria. The source documents that demonstrate conformance with all inclusion and no exclusion criteria must be retained at the investigational site in order to allow Source Data Verification (SDV) during the monitoring process.
- Obtain the subject's medical history
- Perform relevant physical examination
- Obtain the subject's current medications

- Determine subject's NYHA classification
- Obtain a written informed consent

The following procedures must be conducted AFTER inclusion (informed consent) of the subject in the trial

- Collect blood sample if not standard of care
- 12-lead Electrocardiogram (ECG) if not standard of care
- Questionnaire for quality of life (EQ5D)
- Determine subject's STS score and EuroSCORE II if not standard of care
- Determine modified Rankin scale and NIHSS scores

Operative evaluation

The Perceval valve is designed to be anchored in the native annulus using a sutureless technique. The IFU of the Perceval valve is provided in Appendix 2

Information collected during the implant will be recorded on the Operative Case Report Form. These data will include (but not limited to) and will be collected within the eCRF:

- Implant details including surgical approach and valve information
- Surgical procedure including insertion and sizing
- Valve lesion type, pathology, and etiology
- Surgical procedural information
- Concomitant procedures
- Subject outcome
- Cardiac rhythm

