- Echocardiographic examination (TTE) measured at investigational site (MPG; PPG, EOA, DVI, PVL)
- Serious adverse events (as reported in section 17) including all hospitalizations

1 year FUP visit

This visit is for the evaluation of the primary endpoint and is intended to be done as a clinic visit at 1 year \pm 1 month after the day of the surgery. Follow-up evaluations are to be conducted in an office, hospital or clinic setting and are to be performed by the Principal Investigator or designee. If the subject has been seen at another health care facility, the site is to make every effort to obtain the data required for the trial (including copies of source documents) from the subject's offsite physician. All efforts should be made to ensure that the subject comes to the outpatient clinic.

The following data listed below are to be collected:

- Subject status (including NYHA functional classification)
- Physical evaluation
- Medications

- 12-lead electrocardiogram (ECG)
- Modified Rankin Scale and NIHSS assessments
- Blood sample (including WBC, RBC, hemoglobin, hematocrit, platelet count, serum LDH, haptoglobin, reticulocyte, plasma free hemoglobin, serum creatinine and coagulation data)
- Questionnaire for quality of life (recommended)
- Echocardiographic examination (TTE) measured at investigational site (MPG; PPG, EOA, DVI, PVL)
- Serious adverse events (as reported in section 17) including all hospitalizations

2 year FUP visit

This visit is intended to be done between 2 years ± 1 month after the day of the surgery. Follow-up evaluations are to be conducted in an office, hospital or clinic setting and are to be performed by the Principal Investigator or designee. If the subject has been seen at another health care facility, the site is to make every effort to obtain the data required for the trial (including copies of source documents) from the subject’s offsite physician. For this visit telephone follow up is acceptable to collect the clinical information.

The following data listed in **Table 5** below are to be collected according to the type of visit:

Table 5 Data to be collected at 2 year visit according to the type of visit.

Data to be collected	Phone call visit	Outpatient visit
Subject status (including NYHA functional classification)	X	X
Medications	X	X
Blood sample (including WBC, RBC, hemoglobin, hematocrit, platelet count, serum LDH, haptoglobin, reticulocyte, plasma free hemoglobin, serum creatinine and coagulation data)		X

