3. DOCUMENT AND CHANGE HISTORY

3.1.CHANGES IN ANALYSIS COMPARED TO CLINICAL INVESTIGATIONAL PLAN

No changes in the analysis as described in the Clinical Investigational Plan.

3.2.SAP AMENDMENT RATIONALE AND CHANGE HISTORY

Table 2 : SAP Amendment description

Version	Date	Section(s)	Description of modifications
1.0	13MAR2017		Initial Release.
2.0	26JUL2017	7,9,10,10,13	Additional general details on how to represent values in the statistical analysis. Additional specifications have been added to analysis populations (including the definition of adherence to randomization allocation). Details on compliance calculation have been added. Additional derivation rules.
3.0	28JUN2018	10, 11, 12 Editorial changes impact all the document	SAP has been amended following the CIP amendment: 
 Adaptive design; Primary analysis; Sensitivity analysis. Details on primary analysis (Bayesian approach) have been added. Additional analysis for NYHA, echocardiographic data, EQ5D. Surgical times analysis has been modified from ANOVA to ANCOVA. Editorial changes (new template per internal SOP). List of TFLs have been removed (included in a different document).
4.0	16MAY2019	12.1.2, 12.2, 12.3, 13.4	Sensitivity analyses of Surgical times have been added; Additional details for checking the assumptions for ANCOVA; Additional details have been added for the calculation and testing of NCI and rNCI, including the management of missing data (if needed) and an analysis by country; Sensitivity analyses of EQ-5D-5L have been added (using France-based scoring system and with a Mann-Whitney test); The use of a discount rate for the QALY has been removed; Additional details on calculation of EQ-VAS have been added; Details on pacemaker evaluation through ECG Core Lab have been added.

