Descriptive statistics of the change from baseline of the QALY and EQ-5D index values (continuous) at each FU assessment will be shown as described in section 5.2.

Linear mixed model for repeated measures (MMRM) will be applied to compare EQ-5D index values between the two groups. EQ-5D index values will be adjusted by baseline index value, time point, and treatment-by-time interaction. Patient will be also added to the model as a random variable. Estimates of the least square means for EQ-5D index values and 95 % confidence intervals (CIs) will be calculated by each visit and group.

Descriptive statistics of the change from baseline of the EQ VAS data (continuous) at each FU assessment will be shown as described in section 5.2.

Mann-Whitney tests will be applied to compare treatments in terms of EQ-5D index values and EQ VAS data.

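### EQ VAS is compared between arms only by a covariate-free Mann-Whitney test, although a baseline score is scheduled and the EQ-5D index already gets a baseline-adjusted model

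*SAP*

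**What the plan says.** Quality of life at 1 month and 1 year is secondary endpoint 3 (protocol section 8.5.8). EQ VAS is not named there, but SAP section 12.3 analyses it beside the EQ-5D index.

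- **EQ-5D index.** "Linear mixed model for repeated measures (MMRM) will be applied to compare EQ-5D index values between the two groups". The covariates follow: "EQ-5D index values will be adjusted by baseline index value, time point, and treatment-by-time interaction".
- **EQ VAS, description.** "Descriptive statistics of the change from baseline of the EQ VAS data (continuous) at each FU assessment will be shown as described in section 5.2".
- **Both scores, between-arm test.** "Mann-Whitney tests will be applied to compare treatments in terms of EQ-5D index values and EQ VAS data".

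The SAP change history (section 3.2, version 4.0) describes the role of that test: "Sensitivity analyses of EQ-5D-5L have been added (using France-based scoring system and with a Mann-Whitney test".

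On the available data, protocol section 8.7.1 lists "Questionnaire for quality of life (EQ5D") among the procedures required after consent at enrolment, and the flow chart in section 4.2 marks it as done before implant. At 1 year, section 8.7.1 lists it only as "Questionnaire for quality of life (recommended"). On design, protocol section 8.5.7 states: "The randomization will be stratified with 2 stratification factors, by country and by surgical approach".

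No EQ VAS model appears in SAP sections 8.6, 12.3, 14 or 18.12, or in protocol section 10.1.5.

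**The concern.** The Mann-Whitney test entered the SAP as a sensitivity analysis. That fits the index, which has a main model. EQ VAS has no main model, so the sensitivity test is its only between-arm comparison.

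Three things are lost. The comparison is less precise than the scheduled data allow. There is no adjusted treatment difference with a confidence interval for EQ VAS. And because the 1-year questionnaire is only recommended, gaps are foreseeable: a repeated-measures model draws on a patient's other visits, whereas a test at a single visit does not.

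The two randomisation factors enter neither the EQ VAS test nor the index model. Several other SAP models do include them: the logistic sensitivity model (10.4), the Cox model (11), the haemodynamic models (11.2.1) and the surgical-time ANCOVA (12.1.2).

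**Working it through.** **Plan's own figure.** The documents give no power, SD, effect size or correlation for EQ VAS, so there is nothing to reproduce on this point.

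**Inputs from the documents.** Allocation is 1:1. Secondary tests use 0.05 two-sided (protocol section 10.2). Maximum N is 1234. The 10% attrition from enrolment to the per-protocol set (section 10.3) is used here as a stand-in for missing EQ VAS data: 1234 × 0.9 / 2 ≈ 555 per arm.

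**Assumptions, not from the documents.** The baseline-to-follow-up correlation ρ is 0.3 to 0.6, and the unadjusted comparison starts at 80% power. For the figures in points, SD is 18.

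**Step 1: variance of the treatment difference at one visit, equal SDs.**
- Follow-up values: proportional to 1.
- Change scores: 2(1 − ρ).
- Baseline-adjusted: 1 − ρ².

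Adjusted over follow-up values is 1 − ρ². Adjusted over change is (1 − ρ²) / [2(1 − ρ)] = (1 + ρ)/2, which is below 1 for every ρ < 1. Adjustment therefore beats change scores, and beats follow-up values for any non-zero ρ.

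**Step 2: power after adjustment.** Power = Φ[(1.96 + 0.8416)/√R − 1.96], where R is the variance ratio. At ρ = 0.5, R = 0.75 on either reading: 2.8016/0.8660 = 3.235, and Φ(1.275) = 0.90.

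| ρ | R against follow-up values | Power, from 0.80 | R against change | Power, from 0.80 |
|---|---|---|---|---|
| 0.3 | 0.91 | 0.84 | 0.65 | 0.935 |
| 0.5 | 0.75 | 0.90 | 0.75 | 0.90 |
| 0.6 | 0.64 | 0.94 | 0.80 | 0.88 |

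At ρ = 0.2 the gain against follow-up values is only 0.80 to 0.816; it reaches about 5 points near ρ = 0.35.

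**Step 3: detectable difference, 555 per arm, 80% power.** With the t-test, 2.8016 × √(2/555) = 0.168 SD. Under normality the Mann-Whitney test has efficiency 3/π = 0.955, giving 0.168/√0.955 = 0.172 SD. Adjusted, 0.168 × √(1 − ρ²) gives 0.160, 0.146 and 0.135 SD at ρ = 0.3, 0.5 and 0.6. At SD 18 that is 3.1 points against 2.9, 2.6 and 2.4.

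**Step 4: simulation on a bounded scale.** Each setting had 2,000 trials with 555 per arm, means of 62 (baseline) and 75 (follow-up), SD 18, scores rounded and clipped to 0–100, and a true difference of 3.1 points. The adjusted analysis is a single-visit ANCOVA, standing in for the mixed model.

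| Power at ρ | 0.3 | 0.5 | 0.6 |
|---|---|---|---|
| Mann-Whitney, follow-up values | 0.80 | 0.79 | 0.80 |
| Mann-Whitney, changes | 0.62 | 0.75 | 0.83 |
| ANCOVA | 0.85 | 0.89 | 0.94 |
| ANCOVA on ranks | 0.84 | 0.88 | 0.93 |

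Type I error was 0.041 to 0.058 across methods. The simulation standard error at 0.05 is √(0.05 × 0.95/2000) = 0.005, so every method is consistent with 0.05.

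**Stratification factors.** The documents give nothing from which to compute what country and surgical approach would add for EQ VAS or the index. No gain is claimed for them.

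**The case against.** The case for leaving the plan alone has real content.

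- **A rank test is a sound choice for a bounded 0–100 score.** This stands as to validity. It does not defend the absence of baseline: ANCOVA on ranks kept nearly all the gain in the simulation, and the fix retains the Mann-Whitney test.
- **The quality-of-life endpoint already has an adjusted analysis.** This stands. The index, which also feeds the QALY calculation, has one. EQ VAS is a supportive component with no power target or success criterion.
- **The size is assumed.** This stands. Nothing in the documents supports ρ = 0.5 across valve surgery, and the 80% starting point is arbitrary because the trial was sized for MACCE. The detectable differences are small under either method.
- **Chance imbalance is slight at this size.** This stands. The standard error of a baseline difference is √(2/555) = 0.06 SD, which at ρ = 0.5 moves the follow-up comparison by about 0.03 SD.
- **No promise is broken on the strata.** This stands. Protocol section 10.1.5 commits to stratum-adjusted regression for surgical times and consumption indices, not for quality of life.

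A reader might also infer that the baseline score is certainly unused. The documents do not settle that. The test sentence refers to EQ VAS data, while the descriptive sentence before it specifies change from baseline, which suggests follow-up values; but if changes are tested, baseline enters by subtraction. Nor do the documents show that baseline was measured in every patient. They show only that it is scheduled for every patient.

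**Conclusion.** The point holds as a minor one. The only between-arm comparison of EQ VAS is a covariate-free Mann-Whitney test whose input is unstated, while a baseline score is scheduled and an adjusted model is already written for the companion score.

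Against follow-up values, the gain from adjustment is about 4, 10 and 14 points of power, from a start of 80%, at assumed ρ of 0.3, 0.5 and 0.6. Against change scores there is a gain at any ρ below 1. Both statements rest on equal SDs and an assumed ρ. Including the strata rests on consistency with the randomisation and with several other SAP models, not on a computed gain.

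It would be wrong to read this as a biased or invalid test, as a loss of power on the whole quality-of-life endpoint, or as a threat to the non-inferiority conclusion. Type I error is intact, the index is adjusted for baseline, and EQ VAS plays no part in the primary analysis.

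**What to change.** In SAP section 12.3:

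1. Apply the index mixed model to EQ VAS, with baseline EQ VAS, treatment, visit and treatment-by-visit, and report the adjusted difference at each visit with its 95% CI.
2. Include country and surgical approach in both the EQ VAS and the index models, pooling countries with fewer than 20 enrolled patients as SAP section 11 already does.
3. Keep the Mann-Whitney test as a sensitivity analysis, and state whether it uses follow-up values or changes from baseline.

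The cost is a few sentences in the SAP, one extra model run and two added covariates in the index model. No new data are needed.

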13. SECONDARY SAFETY ANALYSIS

Safety data will be summarized descriptively by treatment group.

13.1. ANALYSIS OF ADVERSE EVENTS

A treatment emergent adverse event (TEAE) is defined as any AE that based on start date occurs after implant as defined in Section 5.4. If a non-TEAE worsens after implant, it has to be reported as non-TEAE until worsening and as TEAE afterwards.

A pre-treatment non-TEAEs is an AE starting in the pre-treatment period, a post-treatment non-TEAEs is an AE starting in the post-treatment period as defined in Section 5.4.

If there are partial dates or times, an AE will be considered treatment emergent unless the information available will clearly exclude it. Further details can be found in Section 18.10.

13.1.1. Adverse Events overviews

The following overview tables will be generated by treatment group and overall.

- Summary of the number and percentage of subjects with at least 1
 - Serious TEAE
 - Related serious TEAEs
 - TEAE leading to discontinuation from the study
 - Deaths

The percentage denominator will be the number of subjects.

- Summary of the number and percentage of TEAEs for
 - TEAE
 - Serious TEAE
 - Related serious TEAEs
 - TEAE leading to discontinuation from the study

The percentage denominator will be the total number of TEAEs.

13.1.2. Adverse Events Incidences

The incidence of AE is defined as the number of subjects with occurrence of this AE during the period of interest. The incidence rate (CIR for crude incidence rate) of an AE is defined as the number of subjects with occurrence of this AE during the period of interest divided by the total number of subjects n in the respective group (e.g., treatment group).

The incidence, incidence rate, the number of events and the percentage of events (related to the total number of events) will be summarized by AE term over the entire study post-implant period (from Day 1) and during the early and late phases (section 18.12). For the late events, the incidence rate will be calculated on the number of late patients only.

In addition, safety summaries will be done according to the following plan:

- Intraprocedural and periprocedural (within 72 hours) serious adverse events regardless of relationship with the device.

- All valve and procedure relevant (according to CEC adjudication) serious adverse event composite endpoints and their components as specified in VARC-2 guidelines (and reported in section 18.12):
 - Early safety at 30 days
 - Clinical efficacy after 30 days
 - Time related valve safety annually up to 5 years
- Serious device related (according to CEC adjudication) adverse events up to 5 years (from day 1 up to Day 1826)
- Postoperative site-reported unexpected serious adverse device effect (USADE)
- Site-reported relationship to procedure, device, drug/medication, or other Protocol Required Assessment (section 18.12)
- All late serious adverse events will be analyzed according to a constant hazard model: the linearized rates will be calculated as:
 - total number of late events divided by the total time under evaluation after 30 days (late patient-years).
 - number of patients with at least one late event divided by the total time under evaluation after 30 days (late patient-years).
- The incidence, incidence rate, the number of events and the percentage of Pacemaker (PM) implantation according to:
 - time of occurrence (overall, early, late and up to 1 year), and
 - relationship to device and procedure.

In addition, time-to-event methods (section 5.2) will be used to summarize the time to onset of the following events:

- deaths (overall, cardiovascular, and non-cardiovascular),
- explants and
- all main cardiovascular SAEs:
 - Bleeding,
 - SVD,
 - endocarditis,
 - valve thrombosis,
 - thromboembolic events,
 - stokes,
 - NSVD,

- central leak,
- perivalvular leak,
- thrombocytopenia,
- hemolysis,
- arrhythmias and conduction disorders,
- myocardial infarction, and
- hospitalizations (overall , cardiovascular hospitalization, valve-related hospitalizations);
- First PM implant.

For events leading to hospitalizations, descriptive analysis of the duration will be provided.

The following specific listings will be produced for all enrolled subjects:

- Deaths (the listing will present flags indicating the relevant study phase).
- Serious AEs other than death
- MACCE

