8.5.3 EXCLUSION CRITERIA

Subjects who meet any of the following criteria will be excluded:

1. The subject has a contraindication for treatment by the Perceval valve or by a bioprosthetic aortic valve as stated in the IFU.
2. The subject has aneurismal dilation or dissection of the ascending aortic wall.
3. The subject is scheduled for concomitant procedures other than CABG, myectomy with or without aortic annulus enlargement
4. The subject has congenital bicuspid (i.e. Sievers type 0) or unicuspid aortic valve.
5. Anatomical structures not suitable for Perceval valve such as: aortic root enlargement, where the ratio between the diameter of the sino-tubular junction and the annulus diameter is > 1.3 .
6. The subject has a prosthetic heart valve in any position, including mitral valve repair.
7. The subject has a stroke or myocardial infarction (STEMI and NSTEMI) within 30 days prior to the planned valve implant surgery.
8. The subject has active endocarditis, myocarditis, or sepsis.
9. The subject is in cardiogenic shock manifested by low cardiac output and needing hemodynamic support.
10. The subject is allergic to nickel alloys.
11. The subject is already included in another clinical trial that could confound the results of this clinical investigation.

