8.5.8 TRIAL ENDPOINTS DEFINITION AND ASSESSMENTS

The primary endpoint will be evaluated in a non-inferiority setting, with statistical hypothesis tests formally defined in section 10.

Primary endpoint

The primary endpoint is freedom from MACCE (composite endpoint of all cause death, myocardial infarction, stroke, and valve re-intervention) at one year based on CEC adjudication.

The definitions of each component endpoint are reported in the **Table 4** below, complete definitions can be found in Appendix 4.

Table 4 Definitions of the single endpoint of MACCE

Endpoint	Definition
All cause of death	Total number of deaths regardless of cause (cardiovascular mortality + non cardiovascular mortality)
Myocardial infarction	Myocardial injury as specified in VARC-2 [1]
Stroke	Stroke is defined as an acute episode of focal or global neurological dysfunction caused by the brain, spinal cord, or retinal vascular injury as a result of hemorrhage or infarction. A stroke may be classified as “undetermined” if there is insufficient information to allow the categorization as ischemic or hemorrhagic.
Valve Re-intervention	Any re-intervention, including a transcatheter valve implant, on the implanted aortic valve bioprosthesis after surgical closure of the chest.

Secondary endpoints

1. Surgical time
 - a. Cross clamp time during index procedure
 - b. Cardiopulmonary bypass time during index procedure
2. Normalized Consumption Index and reduced Normalized Consumption Index, including resource consumption items such as (but not limited to):
 - a. Operative room time,
 - b. Duration of ICU/CCU and total hospital stay
 - c. Incidence of specific serious adverse events as defined in Appendix 3
 - d. Blood transfusion(s)
3. Quality of life questionnaire
 - a. At 1 month and 1 year post surgery
4. Intraprocedural and periprocedural serious adverse events regardless of relationship with the device within 72 hours.
5. All valve and procedure relevant serious adverse events as specified in VARC-2 guidelines [1] (Appendix 7)
 - a. Early safety at 30 days
 - b. Clinical efficacy after 30 days
 - c. Time related valve safety: SVD, endocarditis, thrombosis, thromboembolic events (excluding stroke), and bleeding annually up to 5 years
6. Serious device related adverse events up to 5 years
7. Freedom from MACCE at 2, 3, 4 and 5 years of follow up
8. Pacemaker implantation and cause up to 1 year

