MACCE @ n year (Yes/No)	
CEC adjudication of Serious Adverse Event (SAE), Valve re-intervention:
 
YES if at least one per CEC:
 
 - Death (Time to SAE <=n*365.25 days) - Myocardial infarction (Time to SAE <= n*365.25 days) per CEC - Stroke (Time to SAE <= n*365.25 days) per CEC - Reintervention (Time to SAE <= n*365.25 days) 
NO, otherwise

PM implant	
SAE FORM – TREATMENT
 
Yes if:
 
 - Was a pulse generator implanted? = YES - If yes, specify = Pacemaker 
NOTE: PM implant will be classified as intraoperative, early or late according to the date of PM implant (not the AE start date)

Derived variable	Derivation algorithm
Last exposure date	
Study Termination, Serious Adverse Event (SAE):
 
 1. For explant of investigational device: date of explant 2. For dead subjects: date of death 3. For alive and not explanted subjects: 
 - Date of termination - If there is no date of termination, the last available FU date (including discharge) or the last SAE date (occurrence date), whichever occurs later. - If there is no follow-up and no adverse events : date of surgery or date of randomization, whichever occurs later.
Last study date	
Study Termination, Serious Adverse Event (SAE):
 
 1. For dead subjects: date of death 2. For alive subjects: 
 - Date of termination - If there is no date of termination, the last available FU date (including discharge) or the last SAE date (occurrence date), whichever occurs later. 
If there is no follow-up and no adverse events : date of surgery or date of randomization, whichever occurs later.

Study length (days)	
Study termination, Subject Information:
 
Last study date – Enroll Date+1

Extent of exposure (days)	
Last exposure date-surgery date+1

Late patients	
Subjects with more than 30 FU days of exposure

Patient-years	
Cumulative Study length (days)/365.25

Derived variable	Derivation algorithm
Early patient-years	Cumulative Study length (days) up to 30 days/365.25
Late patient-years	Cumulative Study length (days) from 31st day/365.25. Subjects with less than 31 FU days do not contribute to the late patient-years

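### The pacemaker endpoint is not restricted to patients without a pacemaker before surgery and does not separate new implants from replacements; the effect is modest and cheap to correct.

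*SAP*

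**What the plan says.** Protocol 8.5.8 lists "Pacemaker implantation and cause up to 1 year" as secondary endpoint 8, and 8.5.9 adds a core-lab sub-study of patients who receive a pulse generator.

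Protocol 8.5.3 gives eleven exclusion criteria, and none names a pacemaker or defibrillator. The nearest is criterion 6, which concerns valves: "The subject has a prosthetic heart valve in any position, including mitral valve repair". Criterion 1 points outside the protocol: "The subject has a contraindication for treatment by the Perceval valve or by a bioprosthetic aortic valve as stated in the IFU". The IFU (Appendix 2) is not in the supplied text.

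SAP 13.1.2 defines the crude incidence rate as the number of subjects with the event "divided by the total number of subjects n in the respective group (e.g., treatment group", with one exception: "For the late events, the incidence rate will be calculated on the number of late patients only". It then applies this to pacemakers: "The incidence, incidence rate, the number of events and the percentage of Pacemaker (PM) implantation according to" time of occurrence and relationship to device and procedure. The same section plans a time-to-event summary of the first pacemaker implant, without saying how a device already present is treated.

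SAP 18.12, Table 8, derives the event from the treatment part of the SAE form under two conditions. The first is "Was a pulse generator implanted? = YES". The second is that the generator is specified as a pacemaker. There is no condition that the implant be new. The medical history listed in SAP 8.5 does not include a prior device.

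**The concern.** A patient who already has a permanent pacemaker cannot acquire a first one because of the valve. Keeping such patients in the denominator lowers the reported rate in both arms and narrows the absolute difference between a self-anchoring and a sutured valve, which is what a reader of this safety endpoint will look for. Separately, a generator replacement or upgrade in such a patient would count as an event if it were entered on the SAE form as a pacemaker implant, although it may have nothing to do with the valve.

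The early post-implant pacemaker subgroup in SAP 5.3 has the same gap. A patient paced before surgery who receives no further implant falls in the No level, together with patients who have no device.

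**Working it through.** The documents give no expected pacemaker rate, no baseline prevalence and no sample size for this endpoint, so there is no figure of the plan's own to reproduce. The values below are assumptions chosen to show the range.

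**Inputs**
- q, share of subjects with a permanent pacemaker before surgery: assumed 2%, 5%, 10%.
- r, new-pacemaker rate among subjects without one: illustrative 10% in one arm and 5% in the other (difference 5.0 points, ratio 2.0).
- f, share of already-paced subjects whose replacement is recorded on an SAE form as a pacemaker implant: assumed 0% or 10%.
- q and f are taken as equal in the two arms, as randomization would give on average.

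**Formulas**
- Reported rate = (1 - q) × r + q × f.
- Reported risk difference = (1 - q) × (r1 - r2). The term q × f cancels.
- Reported risk ratio = [(1 - q) r1 + q f] / [(1 - q) r2 + q f].

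**Results**

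| q | f | Arm 1 | Arm 2 | Difference (points) | Ratio |
|---|---|---|---|---|---|
| 2% | 0% | 9.80% | 4.90% | 4.90 | 2.00 |
| 5% | 0% | 9.50% | 4.75% | 4.75 | 2.00 |
| 10% | 0% | 9.00% | 4.50% | 4.50 | 2.00 |
| 2% | 10% | 10.00% | 5.10% | 4.90 | 1.96 |
| 5% | 10% | 10.00% | 5.25% | 4.75 | 1.90 |
| 10% | 10% | 10.00% | 5.50% | 4.50 | 1.82 |

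Worked line for q = 5%, f = 10%: arm 1 is 0.95 × 10% + 0.05 × 10% = 10.0%; arm 2 is 0.95 × 5% + 0.05 × 10% = 5.25%; the difference is 4.75 points and the ratio 10.0 / 5.25 = 1.90.

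The table shows three things. Dilution alone shrinks the difference and leaves the ratio alone. Counted replacements leave the difference alone and shrink the ratio. For a single arm's rate the two effects oppose each other and cancel when f = r; in arm 2 with f = 10% the reported rate is above the true 5%.

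**Unequal prevalence.** With 1234 / 2 = 617 per arm, the 95% range of a chance imbalance in q is ±1.96 × sqrt(2q(1 - q)/617), which is about ±1.6, ±2.4 and ±3.4 points for q = 2%, 5% and 10%. At r = 10% this moves the risk difference by about 0.16, 0.24 and 0.33 points, in either direction.

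**Against sampling error.** At 10% versus 5% with 617 per arm, SE = sqrt(0.09/617 + 0.0475/617) = 1.49 points, so the 95% half-width is about 2.9 points. The shrinkage of 0.10 to 0.50 points lies well inside that.

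**The case against.** The strongest case for leaving the plan alone is that an all-subject crude rate is a stated and transparent convention. The endpoint is descriptive (SAP 13), with no test or margin attached, and the shift is a fraction of its sampling error. SAP 13.1.2 also breaks implants down by relationship to device and procedure, and the sub-study in Protocol 8.5.9 collects indication and timing. A careful reader could therefore pick out replacements afterwards. All of this stands as a limit on importance. It does not supply an at-risk rate, because no rule uses that information to filter the event or the denominator.

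Several stronger readings are tempting but not supported:

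- *Any pulse generator counts.* Table 8 also requires that the generator be specified as a pacemaker. The definition that includes defibrillators belongs to the protocol sub-study.
- *Every pacemaker rate divides by all subjects.* Late rates use late patients only, although these still include patients paced before surgery.
- *A planned replacement will be counted.* It counts only if it reaches the SAE form. The SAE definitions (Appendix 4) and the eCRF are not in the supplied text, so the frequency cannot be judged.
- *The first-implant curve keeps paced patients at risk.* The SAP is silent. A replacement could reasonably be read as not being a first implant.
- *Rates are necessarily diluted, and both effects hide a difference in the same way.* The working shows that they act on different measures and oppose each other on each arm's rate.
- *Already-paced patients are certainly eligible.* No listed criterion bars them, but the IFU contraindications cannot be checked.

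**Conclusion.** The point holds as a modest gap in the definition of a secondary safety endpoint. As written, the SAP neither restricts the pacemaker rate to patients who could have a first pacemaker nor limits the event to new implants. With equal baseline prevalence, the absolute difference is understated by the factor (1 - q): 0.10, 0.25 or 0.50 points on an illustrative 5.0-point difference at q of 2%, 5% or 10%. The ratio is unaffected unless replacements are counted. At f = 10% it would fall from 2.0 to 1.96, 1.90 or 1.82.

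These sizes rest entirely on assumed values of q, r and f, on equal q and f in the two arms, and on the IFU not excluding prior devices. The primary endpoint and its non-inferiority analysis do not use this variable. The change is worth making because it gives a rate that answers the clinical question at little cost, not because the stated rate would seriously mislead.

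**What to change.** In SAP 13.1.2 and Table 8:

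1. Add a flag for a permanent device present before surgery. Candidate sources are the preoperative 12-lead ECG with rhythm strip (Protocol 4.2) and the previous cardiovascular procedures mentioned in SAP 12.1.2. First confirm that the eCRF captures prior devices: SAP 8.5 does not list them, and an ECG alone may miss a device that is not pacing when it is recorded.
2. Report the new-pacemaker incidence, and the curve for time to first implant, among subjects without a device before surgery.
3. List replacements and upgrades in subjects who already carried a device separately, outside the event count.
4. Keep the all-patient rate as a second line, so that the currently planned figure is still available.
5. State how flagged subjects are treated in the early-pacemaker subgroup of SAP 5.3.

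The cost is SAP wording and one derived variable, provided the data exist; if they do not, a retrospective query to sites would be needed. The downside is a slightly smaller denominator and a somewhat higher reported rate. At an assumed q of 5%, 617 × 0.95 is about 586 per arm, and a true 10% is reported as 10.0% where dilution alone would give 9.5%.
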